6.1. Tertiary Objective

Active follow up period for study subjects is 12 months after randomization. As a tertiary objective the study will obtain electronically available data up to the end of study recruitment and follow up period, which is 4 years from start of enrollment for the study. Data sources for this objective will be the Suicide Prevention and Application Network (SPAN) and VHA Corporate Data Warehouse (CDW).

Analysis of this passively obtained data will be to:

- 1) describe the pattern of Lithium use following active participation in the study participants,
- 2) evaluate suicide reattempt and all cause mortality over a longer follow up period, and
- 3) evaluate all cause mortality over a longer follow up period.

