- A. Defining inclusion/exclusion criteria and the “indication”: The study includes patients with depression or bipolar disorder who have survived an episode of suicidal self-directed violence, and allows enrollment of patients with psychiatric comorbidities other than psychotic disorders, active substance abuse, and dementia. Basically, the proposal is to test the effectiveness of lithium for prevention of suicide-related behaviors rather than the treatment of any specific condition. The study population for this clinical trial is similar to that of the Lauterbach study (2008) while the Oquendo study (2011), in contrast, studied only patients with bipolar disorder. There may be adequate numbers of patients in VA to support a study limited to depression, but not for one limited to bipolar disorder. Nevertheless, the decision to include all potential subjects with an affective disorder was based on the available evidence and was intended to maximize the potential impact of findings, both for VA and beyond.
- B. Potential limitations in the accuracy of estimates for the number of suicide attempts and reattempts:
 1. Attempt rates: The number of suicide attempts and the number of unique individuals who have survived attempts are identified in real time by the SPCs. The SPCs also report on deaths from suicide when they become aware of them. Comparing these reports of deaths with those identified through the CDC’s National Death Index (after a lag of 2-3 years) demonstrate that facilities are aware of somewhat less than half of all suicides in their population. It is possible that similar limitations in ascertainment apply to suicide attempts as well as deaths, and that the SPC reports may underestimate the number of attempts and the number of survivors. However, ongoing review of the reported attempts has repeatedly demonstrated that there are few, if any, false positives. Therefore, the estimates used for planning this study must be viewed as lower limits for the true numbers of potentially eligible subjects.

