At the end of the study period, we will perform an electronic data sweep to collect passive follow-up data on lithium use and suicide related behaviors following active participation in the study for all subjects that had been randomized. In addition, death rates for individuals who were considered as part of pre-screening activities will be obtained by linking SSN with SPAN, BIRLS and the National Death Index. By the end of the 4 year study period, average follow-up including both active and passive follow up for the study subjects will be 2.5 years (first subject enrolled will have 4 years of follow up and last subject enrolled will have 1 year of follow up). However, subjects terminated from the protocol before they completed a full year of participation will have somewhat longer periods of passive follow-up. Data on lithium use and clinical and administrative data related to primary study endpoints over the extended observation period will be obtained by linking the study database to SPAN data, VA Electronic Medical Records data, VA Pharmacy Benefit Management data, the VA Beneficiary Identification and Records Locator System database, and the VA-DoD data repository for suicide-related data that will include data on causes of death from the National Death Index. Linkage for most variables will be through the VHA Corporate Data Warehouse, a national repository of data from VA Electronic Medical Records and several other VHA clinical and administrative systems.

Hospital admission records and discharge summaries will be collected to determine if a subject was hospitalized to prevent suicide.

XV. MONITORING ADVERSE EVENTS

Role of the Site Investigator and Research Team in Adverse Event Monitoring

The site Research Team is responsible for the following:

1. Closely monitoring all subjects for new adverse events (AEs) and/or serious adverse events (SAEs);
2. Reviewing accuracy and completeness of all AEs and/or SAEs reports.

3. Complying with Cooperative Studies Program policies for reporting AEs and/or SAEs.
4. Complying with local Research & Development Committee (R&DC) policies for reporting AEs and/or Serious AEs.
5. Complying with:
 - a. VA Central IRB (<http://www.research.va.gov/vacentralirb/>)
 - b. VHA Handbook 1058.01 Research Reporting Compliance Requirements
6. Notifying VA Central IRB and local R&DC of safety issues reported to the investigator by the CSP.

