6.2. Tertiary Endpoints

For Tertiary Objective #1 continued use (yes/no) of Lithium is the outcome event of interest.

For Tertiary Objectives #2 the endpoint event is the same as the primary endpoint as described in section **4.2**.

For Tertiary Objective #3, death from any cause is the endpoint event.

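### SAP 6.1 lists fewer death sources for the tertiary follow-up than the protocol does, and neither document allows for the National Death Index lag or sets a censoring rule for passive follow-up

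*SAP*

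**What the plan says.** **SAP 6.1** gives the sources for the passive follow-up: "Data sources for this objective will be the Suicide Prevention and Application Network (SPAN) and VHA Corporate Data Warehouse (CDW"). It ends the observation window at a point "which is 4 years from start of enrollment for the study". It gives no extraction date.

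**SAP 6.2** says that for tertiary objective 2 "the endpoint event is the same as the primary endpoint as described in section" 4.2, so suicide death is one of four components. Objective 3 is death from any cause.

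**SAP 6.3** analyses both by the strategy of SAP 4.3. The time variable there stops at the adjudicated outcome, death, the 12-month date or the last study visit or contact.

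**Protocol XIV (Extended Follow-up)** has a longer list for randomised participants. Besides SPAN, VA electronic records and pharmacy data, it names "the VA Beneficiary Identification and Records Locator System database" (BIRLS) and the "VA-DoD data repository for suicide-related data that will include data on causes of death from the National Death Index". It routes most variables, not all, through CDW. For the pre-screened group, death rates are "obtained by linking SSN with SPAN, BIRLS and the National Death Index". The data sweep is placed at the end of the study period, and average active plus passive follow-up is given as 2.5 years.

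**Protocol VIII, item B.1** reports that comparisons with the "National Death Index (after a lag of 2-3 years) demonstrate that facilities are aware of somewhat less than half of all suicides" in their population.

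**The concern.** After month 12 there are no study visits, apart from a 30-day check, so deaths must come from linked records. By the protocol's account, the reporting that feeds SPAN misses more than half of suicides. The sources that would supply the rest appear in the protocol but not in the SAP. The protocol's own planning figures for mortality (Section II) took deaths and causes from CDC data, not from SPAN.

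Timing is a second and separate problem. An index that arrives 2-3 years late says little about passive follow-up if it is read at the end of the study. Restoring the source without moving the extraction date would leave most of that period uncovered for cause of death.

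At stake are the suicide-death component of tertiary endpoint 2 and the description of long-term follow-up. Lithium may be stopped in this period, and Protocol XIV notes that suicidality may rise after stopping, so the reported rates will attract interest.

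**Working it through.** **Inputs**
- N = 1,862 (Protocol IV); recruitment over 3 years (Executive Summary), taken as uniform, as in Protocol VII.
- Observation to year 4 from start of enrolment (SAP 6.1); first 12 months active.
- One-year suicide death: 0.44%, 0.54% and 0.80% in three VA cohorts (Protocol II). Applying these first-year rates throughout is an assumption; later rates may be lower.
- Composite one-year rate 15% (Protocol VII).
- Facility awareness below 50%; NDI lag 2-3 years (Protocol VIII). I assume that the NDI-based repository has the same lag.

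**1. The plan's own figure.** For entry time e uniform on 0-3, mean follow-up to year 4 = ∫(4 − e)/3 de = 2.5 years, which matches Protocol XIV. Of this 1.0 year is active and 1.5 years passive.
- Total: 1,862 × 2.5 = 4,655 person-years.
- Passive: 1,862 × 1.5 = 2,793 person-years.

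**2. Suicides in the passive period.**
- 2,793 × 0.0044 = 12.3
- 2,793 × 0.0080 = 22.3
- At 50% awareness: 6.1 to 11.2. Awareness is below half, so fewer than about 6-11 would be seen if CDW adds nothing.

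**3. Weight in endpoint 2.** 0.44/15 = 2.9% and 0.80/15 = 5.3%, so suicide is about 3-5% of the composite. Losing half of it removes about 1.5-2.7% of composite events.

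**4. NDI coverage of passive time.** A pull at year S with lag L is complete to c = S − L. For 1 ≤ c ≤ 4, mean passive time before c is (c − 1)²/6, against 1.5 at year 4, so the share is ((c − 1)/3)². Mean total time before c, for c ≤ 3, is c²/6, against 2.5.

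| Pull | Lag | Complete to | Passive share | Total share |
|---|---|---|---|---|
| Year 4 | 2 y | 2.0 | 11.1% | 26.7% |
| Year 4 | 3 y | 1.0 | 0% | 6.7% |
| Year 4.5 | 2 y | 2.5 | 25.0% | 41.7% |
| Year 4.5 | 3 y | 1.5 | 2.8% | 15.0% |

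Year 4.5 is shown because the Executive Summary gives 4.5 years as total study duration. The passive column is the relevant one, since deaths in the active year have other sources. Completeness to year 4 needs a pull at 4 + 2 = 6 to 4 + 3 = 7 years.

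**5. Censoring.** Applied literally, the SAP 4.3 time variable ends at 12 months or the last contact and so removes the passive follow-up. SAP 6.3 puts nothing in its place.

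**The case against.** Several points on the other side stand.

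- **The SAP wording may be shorthand.** The protocol describes CDW as the linkage route for most variables, SAP 6.1 does not say that its list is exclusive, and SAP 1 cites the protocol as a source. A deliberate deletion is therefore not established. But the protocol does not route all variables through CDW, and the SAP lists SPAN separately from CDW, so shorthand cannot be assumed either.
- **No objective stands on suicide death alone.** A reader might infer that such an objective exists and cannot be answered on this timetable. Suicide death is a small part of endpoint 2. The SAP fixes the end of observation, not the date of the data pull, so a later pull is compatible with it. The lag conflict comes from the protocol's end-of-study sweep.
- **The halving does not extend to all 4,655 person-years.** Deaths in the active year reach the study through serious adverse event reporting, medical records or death certificates, and adjudication. Early withdrawals lengthen passive time somewhat beyond 2,793 person-years.
- **The halving does not extend to all-cause mortality.** The awareness figure concerns suicides across the VA population. Neither document states how complete CDW is for vital status.
- **Carrying everyone without a recorded death to year 4 as alive is an inference.** Neither document says so; the rule is simply missing.

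The tertiary analyses are exploratory and follow disclosure of treatment assignment, which limits their weight. None of this removes the mismatch in sources or the missing extraction and censoring dates.

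**Conclusion.** The concern holds in a limited form. The SAP and protocol disagree on the death sources for the tertiary follow-up and must be reconciled. Followed as written, the SAP risks under-counting suicide deaths after month 12. The size in step 2 rests on three assumptions: constant first-year rates, facility awareness that applies to trial participants, and no contribution from CDW. It touches one small component of endpoint 2, and for endpoint 3 no size can be given.

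The lag is a separate defect, inherited from the protocol. With an end-of-study pull, the index would leave at least three quarters of passive person-time without cause of death, and all of it in the worst case. The 2.5-year average is right as elapsed time, but it is not the follow-up covered for cause of death.

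The documents do not support saying that long-term mortality cannot be studied, or that the primary result is affected.

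**What to change.** 1. **SAP 6.1:** name BIRLS and the NDI-based repository as death sources, as in Protocol XIV.
2. **SAP 6.1 and Protocol XIV:** keep the year-4 observation window but state a separate extraction date. For cause of death complete to year 4, this is about years 6-7 from start of enrolment.
3. **SAP 6.3:** replace the SAP 4.3 time variable for tertiary objectives 2 and 3. Censor each endpoint at the date through which its source is complete, within the year-4 window.
4. **Reporting:** give the follow-up actually covered for each endpoint alongside the 2.5-year average.

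The cost is SAP and protocol wording plus a later pull from sources that the protocol already names. The downside is that the tertiary suicide and cause-of-death report comes about 2-3 years after year 4. The primary report is not delayed.

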6.2. Tertiary Endpoints

For Tertiary Objective #1 continued use (yes/no) of Lithium is the outcome event of interest.

For Tertiary Objectives #2 the endpoint event is the same as the primary endpoint as described in section **4.2**.

For Tertiary Objective #3, death from any cause is the endpoint event.

6.3. Statistical Methods for Tertiary Analyses

Tertiary objective#1 will be evaluated by descriptive analysis on duration of lithium use, and by regression methods on any lithium use within one month following active study participation. The latter endpoint (continued use yes/no) will be modelled as a binary outcome to identify determinants and evaluate their association.

Tertiary objectives #2 and #3 will be evaluated following the same analytic strategy as the primary analysis described in section **4.3**.

7. General Considerations

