If lithium treatment prevented approximately 40% of repeated attempts in patients with depression or bipolar disorder during the year after an attempt (see Section VII below), it would prevent almost 600 reattempts. If it prevented approximately 40% of deaths, it would save on the order of 20 lives each year. These estimates (and the others included below) are limited to the effects that would occur during one year of preventive treatment; they do not estimate the potential benefits of longer term maintenance treatment. However, the potential effect of lithium could be far larger. As discussed above, there are approximately 500 deaths from suicide each year in VA patients with depression or bipolar disorder. If lithium treatment were utilized in these patients, it could, in principle, lead to approximately 200 fewer deaths from suicide per year.

In considering the impact of lithium treatment, it is important to consider the potential effects on all-cause mortality among those who have survived a suicide attempt. There is substantial literature demonstrating that individuals who have survived a suicide attempt are at increased risk for death, not just from suicide, but from other forms of unnatural, external, or accidental deaths as well (Bergen et al., 2012; Cooper et al., 2005; Hawton et al., 1988, 2003, 2006; Karasouli et al., 2010; Nordentopf et al., 1993; Owens et al., 2002; Ostamo & Lonnqvist, 2001). One possible explanation for this finding may be that medical examiners and coroners may under-diagnose suicide; another is that there may be shared risk factors for suicide attempts and for death from unnatural causes.

In one preliminary investigation in the VA, 2276 patients who attempted suicide in the first quarter of 2009 were identified from the SPAN data set. Based on CDC data, 3.0% died during the subsequent year, 0.44% of the total died from suicide, and 1.30% from other unnatural causes. In another investigation in VA, 39,803 individuals were identified from medical record data as having survived a suicide attempt between 2000 and 2008. Based on CDC data, 14.8% had died by the end of 2009. 4.7% died within one year after their attempt, 0.80% from suicide

and 0.96% from other unnatural causes. For the 8331 Veterans identified from medical records as attempting suicide in 2008, 0.54% died from suicide in 1 year and 0.71% from other unnatural causes.

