To be conservative, our sample size estimate is based on an initial estimate of a 43% effect, the weighted average of the 48% reduction effect observed in the Lauterbach study and the 33% reduction effect observed in the Oquendo study. We adjusted for a potential attenuation of the effect due to non-adherence; estimating 15% non-adherence leads to a final estimated effect size of 37%. As discussed below, correction for the loss of data from patients who dropout is addressed through estimates of the sample size requirement, not the effect size for the intervention.

Missing Data from Attrition

In randomized clinical trials, Lauterbach (2008) and Oquendo (2011) reported overall attrition rates of 58% and 50% in the lithium group respectively, of which 21% and 11% were treatment related. Moreover, Lauterbach reported a similar rate of attrition for the placebo group, suggesting that there was no differential dropout.

The proposed study, unlike the previous trials, allows for continued enrollment of subjects who discontinue study medications. The sample size calculations are based on a dropout rate during the course of the study of approximately 40%, or assuming that the dropout rate is uniform, a reduction in the effective sample size of approximately 20%. Allowing for up to 40% dropout or approximately a 20% loss of data for reasons unrelated to treatment, the statistical power calculation is based on an effective sample size of 1,490 evaluable patients from a total of 1,862 enrolled. For the primary time to event analysis, we will censor follow up at the first occurrence of the primary endpoint event, death, or withdrawal from the study for any reason.

We will test the missing at random assumption using a Bayesian Pattern Mixture Missingness approach (Rybin et al., 2013), to validate the results and identify potential bias from possible non-random patterns of missing data. For secondary longitudinal analyses, we will evaluate missingness patterns and perform sensitivity analysis based on multiple imputation methods.

Non-Adherence to Study Protocol

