As secondary objectives of the study, lithium efficacy will be evaluated for prevention of subtypes of suicidal self-directed violence, for all suicidal self-directed violence events (even after the first recurrence), for prevention of repeated events in subgroups as well as in the entire sample, and to identify potential mediators.

The tertiary objectives of the study are to extend the follow up period using electronically available data to describe patterns of lithium use following active participation in the study participants, as well as to evaluate rates and determinants of suicide reattempts and all cause mortality over a longer follow up period.

3. Investigational Plan

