4.3. Statistical Methods for Primary Efficacy Analysis

Primary efficacy analysis will include the modified intention to treat sample as defined in section 3.3 above.

The primary hypothesis can be stated as follows.

Under the null hypothesis: The 1-year event rate is 15% and the two treatment groups do not differ in their time to event hazard rates.

Under the alternative hypothesis: The 1-year event rate is 9.45% for patients treated with lithium and 15% for patients in the placebo group, resulting in an absolute reduction from 15% to 9.45% = 5.55% and a relative reduction of $(15 - 9.45)/15 = 37\%$. The group on lithium augmentation has a lower hazard rate than the placebo augmentation group with a hazard ratio for lithium therapy compared to control therapy lower than or equal to 0.61.

We will test this hypothesis with a two sided log rank test at 90% power and 4.8% Type I error (i.e., 5% overall error allows for one interim test at 0.2%). Null hypothesis will be rejected if the hazard ratio exceeds $1/0.61 = 1.64$ or falls below 0.61.

A significant difference showing that the lithium augmentation compared to placebo decreases the hazard of suicidal self-violence will be regarded as a positive result, whereas a result that shows lithium augmentation does not significantly differ from placebo or significantly increases the hazard rate relative to placebo will be regarded as a negative result.

Log rank test will be followed by Cox proportional hazards regression modeling to provide the hazard rates, their ratio and the 95% confidence interval about the ratio.

We will test the proportional hazards assumption by including a time*treatment interaction term in the model and use graphic methods to study goodness of fit as described in Anderson et. al., 1991.

The SAS code for the primary analysis is as follows, where, tx is coded as {1=lithium, 0=placebo}, event is coded as {1=adjudicated outcome, 0=otherwise}, and FUdays is counting number of days from randomization date to the first occurrence of (adjudicated outcome, death, 12 month date, or last study visit/contact date).

Log-Rank Test:

```
title "Survival Estimates by Month";
proc lifetest data=endpt plots=(s); time FUdays*event(0); strata tx; run;
quit;
proc lifetest data=endpt method=life plots=(ls) intervals=30 90 120 150
180 210 240 270 300 330 365; time FUdays*event(0); strata tx; run; quit;

title "Survival Estimates by Month";

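### The extended suicidal-event analysis has no competing-risk estimate: if 1 minus Kaplan-Meier is read as the proportion with an event, it runs about 0.2 to 1.5 points high at 2.5 years and 0.5 to 3 points high by year 4

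*SAP*

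**What the plan says.** SAP section 2 extends follow-up through electronic records in order to "evaluate rates and determinants of suicide reattempts and all cause mortality over a longer follow up period". SAP 6.1 sets the horizon at 4 years from the start of enrollment. Protocol XIV (Extended Follow-up) gives a range of 1 to 4 years and a mean of 2.5.

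On the endpoint, SAP 6.2 states: "For Tertiary Objectives #2 the endpoint event is the same as the primary endpoint as described in section" 4.2, which is the suicidal composite. A death from another cause is not an event. On method, SAP 6.3 states: "Tertiary objectives #2 and #3 will be evaluated following the same analytic strategy as the primary analysis" in section 4.3.

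In SAP 4.3, "event is coded as {1=adjudicated outcome, 0=otherwise", and follow-up time is the "number of days from randomization date to the first occurrence of (adjudicated outcome, death, 12 month date, or last study visit/contact date". Protocol VII (Missing Data from Attrition) agrees: "we will censor follow up at the first occurrence of the primary endpoint event, death, or withdrawal from the study for any reason". The 4.3 code runs `proc lifetest` for survival estimates by arm, with life-table intervals ending at day 365, then the log-rank test and Cox models.

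Neither document mentions competing risks or cumulative incidence.

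**The concern.** A participant who dies of another cause can no longer have a suicidal event. Censoring that person is appropriate for comparing cause-specific hazards. It is not appropriate for estimating what share of these Veterans go on to have an event, because 1 minus Kaplan-Meier then describes a setting in which nobody dies of anything else.

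The cohort has appreciable other mortality. For one VA cohort of attempt survivors, Protocol II reports: "14.8% had died by the end of 2009. 4.7% died within one year after their attempt, 0.80% from suicide". Over 12 months this hardly matters. Over several years the gap widens, and the survival estimates are the only output of the 4.3 strategy that gives event probabilities over time. At stake is the accuracy of any long-term absolute risk presented from this trial, not a test or a hazard ratio.

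**Working it through.** **Inputs from the documents**
- First-year event rates: 15% placebo, 9.45% lithium (SAP 4.3). Hazards: −ln(0.85) = 0.1625 and −ln(0.9055) = 0.0993 per year. Their ratio is 0.611, matching the plan's 0.61.
- Mean follow-up: (1 + 4)/2 = 2.5 years, as the protocol states.
- One-year non-suicide mortality (Protocol II): 3.0% − 0.44% = 2.56% in one cohort, and 4.7% − 0.80% = 3.9% in another. Hazards: 0.0259 and 0.0398.

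The plan states no long-term event rate, so there is no such figure to reproduce.

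**Assumptions**
- After year 1 the event hazard is k times the first-year hazard, with k = 1, 1/2 or 1/3.
- Non-suicide mortality is constant at 1.8%, 2.56% or 3.9% per year. The 1.8% allows for the trial's exclusion of heart failure and eGFR below 60; it is not in the documents.

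**Formulas.** With event hazards h₁ (year 1) and h₂ = k·h₁ (later), and death hazard d, for T > 1:
- 1 − KM = 1 − exp(−h₁ − h₂(T − 1))
- CIF = [h₁/(h₁+d)]·[1 − exp(−(h₁+d))] + exp(−(h₁+d))·[h₂/(h₂+d)]·[1 − exp(−(h₂+d)(T − 1))]

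**One case in full.** Placebo, k = 1, 2.56% mortality, T = 4:
- 1 − KM = 1 − exp(−0.650) = 47.8%
- CIF = (0.1625/0.1885)·(1 − exp(−0.754)) = 45.7%
- Excess = 2.1 points

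**Excess of 1 − KM over CIF, in points** (mortality 1.8% / 2.56% / 3.9% per year)

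| First-year rate | k | 2.5 years | 4 years |
|---|---|---|---|
| 15% | 1 | 0.70 / 0.99 / 1.50 | 1.51 / 2.14 / 3.23 |
| 15% | 1/2 | 0.43 / 0.62 / 0.94 | 0.93 / 1.31 / 1.98 |
| 15% | 1/3 | 0.34 / 0.48 / 0.73 | 0.69 / 0.97 / 1.47 |
| 9.45% | 1 | 0.47 / 0.67 / 1.01 | 1.09 / 1.54 / 2.32 |
| 9.45% | 1/2 | 0.29 / 0.41 / 0.62 | 0.63 / 0.89 / 1.34 |
| 9.45% | 1/3 | 0.22 / 0.31 / 0.48 | 0.46 / 0.65 / 0.98 |

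At 12 months the excess is 0.08 to 0.29 points.

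**Arm difference at year 4**, k = 1, supposing the planned effect persists: 47.8 − 32.8 = 15.0 points by Kaplan-Meier, against 14.6, 14.4 and 14.1 by cumulative incidence at the three mortality rates. The largest change is 0.9 points.

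**Can 3.9% per year persist?** That cohort attempted in 2000–2008, and 14.8% had died by the end of 2009. If entry was uniform (assumption), time to that date runs from 1 to 10 years. Solving 1 − (e^(−λ) − e^(−10λ))/(9λ) = 0.148 gives λ ≈ 0.030 per year for all causes. Applying the year-1 cause split, 0.030 × 3.9/4.7 ≈ 0.025 per year for non-suicide death. The right-hand values in the table are therefore upper limits.

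**The case against.** The strongest reply is that no document names 1 minus Kaplan-Meier as the long-term figure to be reported. Protocol VII calls the tertiary objectives exploratory and describes survival analysis and Cox modelling of correlates. The rates in SAP section 2 could mean hazard or person-time rates, which censoring at death does not distort. The life-table intervals and the follow-up definition both stop at 12 months, so the code cannot be carried forward unedited. No tertiary risk difference or subgroup rate is planned, and the minimum content of the final report (SAP 11) is the primary analysis. All of this stands, and it is why the point is conditional on how the survival estimates are read. It does not remove the gap: the strategy being reused includes those estimates, and nothing else in it gives event probabilities.

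The second reply concerns size. The upper figures need the placebo rate, an undiminished event hazard and 3.9% yearly mortality all to continue. Under the planned effect the pooled first-year rate is about 12.2% ((15 + 9.45)/2), and with uniform entry over 3 years and an end at 4 years only about one sixth of participants (0.5/3) reach 3.5 years. This also stands; the ranges must be read as assumption-based.

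Third, a reader might infer that the published long-term rates would be too high on balance. The documents do not support that. Extended data are passive, and Protocol VIII (B.1) says facilities know of somewhat less than half of suicides and that attempts may be missed similarly. This pushes rates down and could exceed the bias described here.

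**Conclusion.** The point holds as a gap in an exploratory analysis. The reused strategy censors non-suicide deaths over up to 4 years, rates are a stated aim, and no cumulative incidence is planned. The direction of this one component is certain: cumulative incidence weights each event by survival free of both event and death, which cannot exceed the Kaplan-Meier weight. The size is not certain. It is about 0.2 to 1.5 points at 2.5 years and 0.5 to 3 points by year 4 under the stated assumptions, with no event hazard after month 12 in the documents to narrow it.

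A reader might go further and infer that the primary result or the treatment comparison is compromised. Neither follows. The 12-month excess is at most 0.3 points, the log-rank test and Cox model remain valid as cause-specific comparisons, and the arm difference moves by under 1 point. The priority is low.

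**What to change.** In SAP 6.3:
- Define follow-up time for the extended analysis so that it runs past the 12-month date. The 4.3 definition has to be rewritten for this purpose in any case.
- Code status as 0 = censored, 1 = suicidal event, 2 = non-suicide death. Report Tertiary Objective 2 event probabilities as Aalen-Johansen cumulative incidence (`proc lifetest` with `eventcode=1`).
- Keep the log-rank test and cause-specific Cox model for comparisons and determinants, with codes 0 and 2 both treated as censored. Keep Kaplan-Meier for Objective 3, where death from any cause is the event.

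In SAP 6.1, which names only SPAN and the Corporate Data Warehouse, add the National Death Index cause-of-death source already listed in Protocol XIV (Extended Follow-up). It is needed to separate suicide from other deaths.

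The cost is a few sentences and a recoded status variable. No new data collection or design change is needed. This does not address under-ascertainment in passive data, which should be stated as a separate limitation.
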